# 6.4 Follow-up Phase

Group 1: Subjects in Group 1 will enter the follow-up Phase when they meet criteria to re-start ART and will be seen 4, 12, and 24 weeks after restarting ART to ensure viral suppression has been achieved.

Group 2: Subjects in Group 2 will enter the follow-up Phase after their final 3BNC117/10-1074 infusion and will be seen 4, 12, and 24 weeks after the last antibody infusion.

At these visits, subjects in both groups will undergo the following procedures:

- Interval medical history and a targeted physical examination, including weight, vital signs, and a symptom-directed evaluation based on symptoms or complaints reported by each subject
- Assessment of any new or unresolved AEs or intercurrent illnesses
- Blood collection for:
  - CBC with differential
  - Chemistry panels, to include: ALT, AST, ALP, creatinine, total and direct bilirubin, and serum albumin levels
  - Flow cytometry panel (includes CD4+ T cell count)
  - Plasma HIV viral level
  - HIV genotype (Group 1; if viral level is >1,000 copies/ml)
  - Storage of serum, plasma and PBMCs

Subjects in Group 2 will also have optional blood draw visits for CD4 counts, plasma viral level, and storage at 2, 6, 8, 10, 16, and 20 weeks after the last antibody infusion which may be drawn at NIH or offsite.

For participants who are unable to return to the NIH CC during the COVID-19 pandemic due to travel restrictions, blood samples may be collected at their local clinics or Quest Diagnostics and sent to the NIH CC for testing which will include; CBC with differential, plasma HIV viral level, and flow cytometry. Chemistry panels may be run at Quest Diagnostics laboratories and the

results sent to the NIH Study team. A study provider (Nurse Practitioner, Physician's Assistant, or Physician) will contact participants by phone and obtain an interval medical history.

#### 7 STUDY EVALUATIONS

## 7.1 Clinical Evaluations

Subjects will undergo a medical history and physical examination.

# 7.2 Laboratory Evaluations

# 7.2.1 Clinical and Research Laboratory Evaluations and Specimen Collection

- HIV viral RNA levels
- HIV genotype (if viral level is >1,000 copies/ml)
- Flow cytometry with CD4+ T cell count
- Routine serologic, hematologic, and clinical chemistry evaluations as described in Section 6

Leukapheresis: Will be performed for research studies including, but not limited to, measurements of the frequency of CD4+ T cells carrying HIV proviral DNA, cell-associated RNA, and replication-competent virus by quantitative co-culture assays. These studies will address the exploratory endpoints. If leukapheresis cannot be performed for technical reasons (e.g., poor venous access), 80 ml of blood will be drawn instead.

Other research evaluations measuring the effect of 3BNC117 and 10-1074 on the HIV pathogenesis may include:

- Frequency of CD4+ T cells carrying HIV proviral DNA and cell-associated HIV RNA
- Levels of cell-associated infectious virus
- Sequencing of viral DNA and RNA
- Neutralization assays using replication-competent HIV against bNAbs
- Frequency of HIV-specific CD4+ and CD8+ T cells
- Markers of T-cell activation, immune exhaustion, and inflammation

#### 8 POTENTIAL RISKS AND BENEFITS

#### 8.1 Potential Risks

## General Risks of MAb Treatment

Administration of mAb may have a risk of immune reactions such as acute anaphylaxis, serum sickness and the generation of antibodies; however, these reactions are rare and more often associated with mAb targeted to human proteins or with the use of chimeric human-murine mAbs, which would have a risk of human anti-mouse antibodies. Both 3BNC117 and 10-1074 are targeted to a viral antigen and are human mAbs; thus, it is expected these mAbs will have a low risk of such side effects. VRC01, a human bNAb that, like 3BNC117 and 10-1074, targets HIV pp120 has been well tolerated in Phase I/II studies with no safety concerns identified .

Typically, the side effects of mAbs are mild but may include fever, chills, rigors, nausea, vomiting, pain, headache, dizziness, shortness of breath, bronchospasm, hypotension, hypertension, pruritus, rash, urticaria, angioedema, diarrhea, tachycardia or chest pain. Most infusion-related events occur within the first 24 hours after beginning administration. Severe reactions, such as anaphylaxis, angioedema, bronchospasm, hypotension and hypoxia, are infrequent and more often associated with mAbs targeted to human proteins or when a nonhuman mAb, such as a chimeric murine mAb, is used.

Delayed allergic reactions to a mAb may include a serum sickness type of reaction, which is characterized by urticaria, fever, lymph node enlargement, and joint pains. These symptoms may not appear until several days after the exposure to the mAb and is noted to be more common with chimeric types of mAbs.

# Analytical treatment interruption (ATI)

The risks from an ATI, performed under close virologic and immunological monitoring are minimal in this subject population. There is a theoretical risk that ATI could lead to the development of HIV drug resistance. This may be a particular concern for individuals taking NNRTIs. However, this potential risk with NNRTIs is essentially eliminated by undertaking the procedures described in Section 3.1. Given the study population, the frequency of immunological and virologic monitoring, and strict criteria for restarting ART, it is extremely unlikely that the ATI will lead to the development of any opportunistic infections or AIDS-defining conditions.

During the ATI phase, subjects may transmit HIV infection if they do not adhere to safe sex practices.

## Phlebotomy/Insertion of IV Catheter

This may be associated with discomfort, bruising, local hematoma formation and, on rare occasions, infections, lightheadedness, and fainting.

The amount of blood drawn for research purposes will be within the limits allowed for adult subjects by the NIH Clinical Center (Medical Administrative Policy 95-9: Guidelines for Limits of Blood Drawn for Research Purposes in the Clinical Center: http://cc-internal.cc.nih.gov/policies/PDF/M95-9.pdf).

### **Leukapheresis**

The potential risks associated with leukapheresis include lightheadedness, dizziness, possible fainting, tingling around the mouth and in the fingers and toes, nausea, chills, vomiting, mild muscle cramps, loss of <1 pint of blood, or pain, bruising, or discomfort at the needle insertion sites. More serious, but rare, complications include nerve damage at the needle insertion site, seizures and air embolism. Most procedures are performed without an incident. Blood components removed during leukapheresis are generally replaced by the body within a few hours or a few days. No infections associated with this procedure have been reported in thousands of cases performed over the last 10 years at the NIH.

# **HLA typing**

Some HLA types have been associated with an increased risk of certain diseases like arthritis and other rheumatologic disorders, or a faster progression to AIDS. HLA typing will be performed on samples collected from all the enrolled subjects. Results from the HLA typing will become part of each subject's medical record at NIH. Medical records containing this information are maintained in a secure place.

#### 8.2 Potential Benefits

Study subjects may not receive direct health benefit from study participation or study infusions. Others may benefit from knowledge gained in this study that may aid in the development better HIV treatments.

# 9 RESEARCH USE OF STORED HUMAN SAMPLES, SPECIMENS OR DATA

- Intended Use: Stored blood samples and data collected under this protocol may be
  used to study the effect of bNAb treatment and ATI on the virologic and immunologic
  parameters listed in Section 7.2.1. Samples may also be used to study other aspects of
  the immunopathogenesis of HIV infection or measure serum levels of antiretroviral
  agents during ATI.
- **Storage:** Access to stored samples will be limited using a locked room or a locked freezer. Samples and data will be stored using codes assigned by the investigators. Data will be kept in password-protected computers. Only investigators will have access to the samples and data.
- **Tracking:** Samples will be tracked utilizing the repository operated by Leidos Biomedical, Inc. Data will be stored and maintained in the NIAID CRIMSON database.
- **Disposition at the Completion of the Protocol:** At the completion of the protocol (termination), samples and data will either be destroyed, or after Institutional Review Board (IRB) approval, transferred to another existing protocol.
- Reporting the Loss or Destruction of Samples/Specimens/Data to the IRB:
  - Any loss or unanticipated destruction of samples or data (for example, due to freezer malfunction) that meets the definition of Protocol Deviation and/or compromises the scientific integrity of the data collected for the study, will be reported to the NIH IRB.
  - Additionally, subjects may decide at any point not to have their samples stored.
     In this case, the PI will destroy all known remaining samples and report what was done to both the subject and to the IRB. This decision will not affect the subject's participation in this protocol or any other protocols at NIH.

# 10 DATA SHARING PLAN

#### What data will be shared?

We will share human data generated in this study for future research as follows:

- De-identified data in an NIH-funded or approved public repository.
- Identified data in the Biomedical Translational Research Information System (BTRIS).
- De-identified or identified data with approved outside collaborators under appropriate agreements.

#### How and where will the data be shared?

Data will be shared through:

- Approved outside collaborators under appropriate individual agreements.
- Publication and/or public presentations.

#### When will the data be shared?

At the time of publication or shortly thereafter.

#### 11 REMUNERATION PLAN FOR SUBJECTS

Eligible subjects will be compensated for travel according to the NIAID/NIH travel policy. Subjects will receive financial compensation for time and inconvenience according to the NIH Clinical Center volunteer guidelines: screening (\$50), leukapheresis (\$200 for a 2-pass leukapheresis procedure), research blood draw (\$40), clinic visits (\$30), 3BNC117/10-1074 infusion (\$80). If subject does not qualify or declines leukapheresis, an additional 80 mL research blood will be drawn and subject may be compensated an additional \$25 for inconvenience. For participants who complete all the follow up phase visits, there is a \$200 completion bonus.

#### 12 ASSESSMENT OF SAFETY

# 12.1 Documenting, Recording, and Reporting Adverse Events

At designated visits with the subject, information regarding AEs will be elicited by appropriate questioning and examinations, and it will be:

- Immediately documented in the electronic database and medical record.
- Reported as outlined below (e.g., IND sponsor, IRB, Food and Drug Administration [FDA]).

#### 12.2 Definitions

#### Adverse event (AE)

An AE is any untoward or unfavorable medical occurrence in a human subject, including any abnormal sign (e.g., abnormal physical exam or laboratory finding), symptom, or disease temporally associated with the subject's participation in the research, whether or not considered related to the research.

## Adverse reaction (AR)

An adverse reaction (AR) is an AE that is caused by an investigational agent (drug or biologic).

## Suspected adverse reaction (SAR)

A suspected AR (SAR) is an AE for which there is a reasonable possibility that the investigational agent caused the AE. 'Reasonable possibility' means that there is evidence to suggest a causal relationship between the drug and the AE. A SAR implies a lesser degree of certainty about the causality than an AR, which implies a high degree of certainty.

# Serious adverse event (SAE)

An SAE is an AE that results in one or more of the following outcomes:

- Death
- A life-threatening (i.e., an immediate threat to life) event
- An inpatient hospitalization or prolongation of an existing hospitalization
- A persistent or significant incapacity or substantial disruption of the ability to conduct normal life functions
- A congenital anomaly/birth defect
- A medically important event\*

\*Medical and scientific judgment should be exercised in deciding whether expedited reporting is appropriate in other situations, such as important medical events that may not be immediately life threatening or result in death or hospitalization, but they may jeopardize the subject or may require intervention to prevent one of the other outcomes listed above.

# **Unexpected adverse event**

An AE is unexpected if it is not listed in the IB or package insert (for marketed products), or it is not listed at the specificity or severity that has been observed. It is the responsibility of the IND sponsor to make this determination.

# Serious and unexpected suspected adverse reaction

A serious and unexpected suspected AR (SUSAR) is a SAR that is both serious and unexpected.

### **Unanticipated problem**

An unanticipated problem (UP) is an event, incident, experience, or outcome that is—

- 1. Unexpected in terms of nature, severity, or frequency in relation to
  - a. The research risks that are described in the IRB-approved research protocol and informed consent document; IB, or other study documents; and
  - b. The characteristics of the subject population being studied; and
- 2. Related or possibly to participation in the research; and
- Suggests the research places subjects or others at a greater risk of harm (including physical, psychological, economic, or social harm) than was previously known or recognized (per the IND sponsor, an AE with a serious outcome will be considered increased risk).

# Unanticipated problem that is not an adverse event (UPnonAE)

An UP that is not an AE (UPnonAE) is an incident, experience, or outcome that is not associated with an AE, which meets the 3 criteria of a UP. Examples include breaches of confidentiality, accidental destruction of study records, and unaccounted-for study drug.

#### **Protocol Deviation**

Any change, divergence, or departure from the IRB approved study procedures in a research protocol. Protocol deviations (PD) are designated as serious or non-serious and further characterized as:

- Those that occur because a member of the research team deviates from the protocol
- Those that are identified before they occur, but cannot be prevented
- Those that are discovered after they occur

**Serious:** A UP or PD is serious if it meets the definition of a Serious Adverse Event (see above) or if it compromises the safety, welfare or rights of subjects or others.

**Non-compliance:** The failure to comply with applicable NIH HRPP policies, IRB requirements, or regulatory requirements for the protection of human subjects. Non-compliance is further characterized as:

- 1. Serious: Non-compliance that
  - a. Increases risks, or causes harm, to subjects
  - b. Decreases potential benefits to subjects
  - c. Compromises the integrity of the NIH-HRPP
  - d. Invalidates the study data
- 2. Continuing: Non-compliance that is recurring
- 3. Minor: Non-compliance that, is neither serious nor continuing.

# 12.3 Investigator Assessment of Adverse Events

If a diagnosis is clinically evident (or subsequently determined), the diagnosis rather than the individual signs and symptoms or lab abnormalities will be recorded as the AE.

All AEs occurring from the time when the first infusion is administered through the specified study follow-up period will be documented, recorded, and reported. The PI will evaluate all AEs with respect to **Seriousness** (criteria listed above), **Severity** (intensity or grade), and **Causality** (relationship to study agent and relationship to research) according to the following guidelines.

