## Analytical treatment interruption (ATI)

After study day 3, all subjects in **Group 1** will stop ART to determine if treatment with 3BNC117 and 10-1074 can prevent plasma viral rebound. Individuals taking non-nucleoside reverse transcriptase inhibitors (NNRTIs) will switch to a protease or integrase inhibitor-based regimen at least 2 weeks prior to week 0 to ensure that the washout period of antiretroviral agents is roughly equal. During the ATI/Treatment phase of the study, HIV RNA levels and CD4+ T cell counts will be monitored every 2 weeks.

Group 1 subjects will be instructed to restart ART if they meet one or more of the following criteria during the ATI phase:

[figure not shown]
- A confirmed >30% decline in baseline CD4+ T cell count or an absolute CD4+ T cell count <350 cells/mm^3 that is associated with a HIV RNA level >40 copies/ml.
- A sustained (>4 weeks) HIV RNA level of >1,000 copies/mL
- Any HIV-related syndrome (e.g. acute retroviral syndrome, opportunistic infection)
- Pregnancy

Subjects who meet one or more of the above criteria during the ATI/Treatment Phase will not receive additional antibody/placebo infusions and enter the follow-up phase (Figure 1). Subjects who have not met criteria to restart ART by week 28 may continue the ATI and have HIV RNA levels and CD4+ T counts monitored every 2 weeks until they either meet criteria to restart ART or reach study week 64 (see Section 6.4).

Subjects in **Group 2** will have their plasma viremia and CD4+ T counts monitored every 2 weeks and will be removed from the treatment phase of the study if they meet any of the following criteria:

- A confirmed >30% decline in baseline CD4+T cell count or an absolute CD4 cell count <350 cells/mm^3
- A sustained (>4 weeks) 0.5log10 increase in baseline HIV RNA level
- Opportunistic infection
- Pregnancy

Figure 1: Study Outline

\* Placebo for Group 1 only

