#### 6.2 Enrollment/Baseline

The enrollment visit may take place over 2 visits to accommodate the baseline pre-treatment apheresis procedure. The first dose of 3BNC117 and 10-1074 or (for Group-1) normal saline placebo will be administered at this visit, and enrollment is defined as the day of receipt of the first study infusions.

Subjects will undergo the following procedures (prior to the first dose of the study antibodies or saline placebo):

- Medical history and physical examination, including weight and vital signs
- Ophthalmologic Exam (within 8 weeks prior to first study infusion)
- Assessment of concomitant medications
- HIV transmission risk behavior assessment and counseling
- Leukapheresis (optional) for research studies
- Blood collection for:
  - Flow cytometry panel (includes CD4+ cell count)
  - o Plasma HIV viral RNA levels
  - HLA typing (if not already on file)

- Storage of plasma, serum and PBMCs
- o CBC with differential
- Chemistry panels, to include: ALT, AST, ALP, creatinine, total and direct bilirubin, and serum albumin levels
- Serum or urine pregnancy test (for women of child-bearing potential-obtained within 24 hours prior to infusion)

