# 12.6 Follow-up of Adverse Events and Serious Adverse Events

AEs that occur following enrollment of subjects (i.e., after the first dose of bNAb or placebo) are followed until the final outcome is known or until the end of the study follow-up period.

SAEs that that are assessed by the investigator to be possibly, probably, or definitely related to study agent/placebo and that have not resolved by the end of the follow-up period will be followed until the final outcome is known. If it is not possible to obtain a final outcome for an SAE (e.g. the subject is lost to follow up), the reason a final outcome could not be obtained will be recorded by the investigator on the AE Case Report form.

SAEs that occur after study completion that are reported to and are assessed by the investigator to be possibly, probably, or definitely related must be reported to the CSO, as described above.

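### AE recording opens at the first infusion, so harm with onset before day 0 from the trial-imposed NNRTI switch or the optional pre-treatment leukapheresis falls outside routine AE recording, and the duty to report a pre-infusion SAE is unclear

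*Combined protocol and SAP*

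**What the plan says.** Section 12.3 states the window: "All AEs occurring from the time when the first infusion is administered through the specified study follow-up period will be documented, recorded, and reported". The same section asks the investigator to judge each event's relation to the study agent and, separately, to the research.

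Section 12.6 uses the same start for follow-up: "AEs that occur following enrollment of subjects (i.e., after the first dose of bNAb or placebo) are followed until the final outcome is known". Section 6.2 ties this to enrollment: "enrollment is defined as the day of receipt of the first study infusions".

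Section 12.2 defines an AE more broadly, as an untoward occurrence "temporally associated with the subject's participation in the research, whether or not considered related to the research".

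Two interventions are scheduled before that start:

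- **ART switch.** Section 3.1: "Individuals taking non-nucleoside reverse transcriptase inhibitors (NNRTIs) will switch to a protease or integrase inhibitor-based regimen at least 2 weeks prior to week 0". The stated purpose is to make drug washout roughly equal across subjects.
- **Leukapheresis.** Section 6.2 lists an optional procedure before the first dose, possibly at a separate visit. Appendix B places it after screening and before the first infusion in both groups. Section 8.1 says of its risks: "More serious, but rare, complications include nerve damage at the needle insertion site, seizures and air embolism".

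Section 15.1 requires consent before any research procedure.

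**The concern.** A person who has consented and then changes regimen or undergoes apheresis for the trial is already a research subject. If harm from either begins before day 0, the stated rule does not call for it to be recorded as an AE. The same apheresis complication at week 16 would be recorded.

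Two things are at stake. The trial's account of harm from its own procedures would be incomplete. Oversight would also be uncertain: the sponsor's safety office and the DSMB receive events that have been identified as SAEs or unanticipated problems, and nothing before day 0 reliably starts that process. Someone harmed before day 0 and never infused would not count as enrolled, so the event could be missing from any table built on enrolled subjects.

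**Working it through.** The plan gives no figure to reproduce, so the check sets the timeline against the reporting rules.

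**Timeline**

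| Step | Timing | Source | Inside the 12.3 window? |
|---|---|---|---|
| Consent, screening | Screening up to 8 weeks before enrollment | 6.1, 15.1, Appendix B | No |
| NNRTI switch (Group 1 subjects on NNRTIs) | At least 2 weeks before week 0 | 3.1, Appendix B | No |
| Optional leukapheresis #1 | After screening, before first infusion | 6.2, Appendix B | No |
| First infusion, which is also enrollment | Day 0 | 6.2 | Window opens |
| ART stop (Group 1) | After day 3 | 3.1, 6.3 | Yes |
| Later aphereses | Week 16 and around week 24; follow-up week 24 in Appendix B | 6.3, Appendix B | Yes |

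For a switched subject, the time on the new regimen before recording starts is at least 2 weeks.

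**Is there an exception elsewhere?** No section extends routine AE recording back to consent or exempts procedure-related events. Section 12.1 elicits AEs at designated visits. The Appendix B flow sheets mark AE assessment from the Day Zero column onward and leave the switch and pre-treatment apheresis columns blank.

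**Could another route catch the event?**

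- *SAE rule (12.4.2).* No start time is stated. Read with 12.2, it could cover a pre-infusion SAE; read with 12.3, it need not.
- *DSMB (12.13).* All SAEs and unanticipated problems go to the Board, again with no start time, so the same ambiguity carries over.
- *Unanticipated problem (12.2, 12.4.3, 12.5).* The event must be unexpected in nature, severity or frequency relative to the described risks. Section 8.1 describes no risk of switching to a protease or integrase inhibitor, so a switch reaction might qualify. The listed leukapheresis complications are described risks and would qualify only if their severity or frequency were unexpected.

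**What is exposed.** Among planned enrolled subjects, switches number between 0 and 30 (all of Group 1). Pre-treatment aphereses number between 0 and 30 + 15 = 45. Neither actual count is given, and people never infused would be additional. The documents give no event rate for either intervention, so no expected number of unrecorded events can be calculated.

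**Effect on the primary endpoint.** Section 3.2.1 counts events of grade 3 or higher judged at least probably related to the test article. Harm that begins before any dose cannot qualify. The endpoint, Table 1 and Table 2 are unchanged.

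**The case against.** The strongest reply is that starting AE collection at first dose is a deliberate choice, stated consistently in 12.3 and 12.6. A definition of an AE and a collection window serve different purposes, so there is no formal contradiction. Events before dosing say nothing about the antibodies, which are the subject of the primary objective. Section 6.2 also requires a history, examination, medication review, blood count and chemistry before the first dose, and Appendix B marks AE assessment on Day Zero. An earlier event in someone who is then infused should therefore appear somewhere in the record.

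Most of this stands, and it limits the point. It does not remove it. An entry in the medical history is not an AE graded for severity and judged for relation to research, and a person who is never infused may not reach the Day Zero assessment.

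Three stronger readings are tempting, and the documents do not support them:

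- *That pre-infusion harm would never be recorded or reported.* The SAE and DSMB rules have no start time, and unanticipated problems go to the IRB under Policy 801 with no dosing condition. That policy and the Safety Review and Communications Plan are not in the documents, so an absolute negative cannot be shown.
- *That at least a quarter of aphereses go unrecorded.* One in four (25%) is the schedule for a subject who has all four in Appendix B. The procedure is optional, Section 6.4 does not list the fourth, and someone who declines the first contributes none. The fraction also counts procedures, not harms.
- *That all harm from the switch is missed.* Switched subjects stay on the new regimen until after day 3, and a reaction that begins after the first infusion is inside the window.

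**Conclusion.** The point holds in a limited form. Routine AE recording does not cover harm with onset between consent and day 0 from the NNRTI switch or the optional leukapheresis, and the text leaves unclear whether a pre-infusion SAE must be reported. The unanticipated-problem route may catch unexpected events, but not reliably the leukapheresis complications that Section 8.1 already lists.

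The loss is in the completeness of safety data and in oversight of research procedures. It does not bias the primary endpoint or affect the power calculation. Its size is unknown and may be small, since serious apheresis complications are described as rare.

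The conclusion assumes that no document outside the protocol, such as the Safety Review and Communications Plan or Policy 801, already requires recording from consent. If one does, the remaining task is a cross-reference. In a small trial whose primary objective is safety, this is a cheap improvement worth making.

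**What to change.** Amend 12.3 and 12.6, and cross-refer from 12.4.2, so that:

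1. From signature of consent, all SAEs are recorded, together with all AEs related to any research procedure or to the trial-imposed ART switch. Name optional leukapheresis explicitly; wording limited to protocol-required procedures would leave out its non-serious events.
2. All other AEs are recorded from the first infusion, as now.
3. Pre-infusion events are tabulated separately, including those in people who are never infused, so that the study-agent safety analysis is unchanged.

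To match, mark AE assessment in the switch and pre-treatment apheresis columns of Appendix B.

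The cost is a short text change, a pre-infusion AE form, and a few extra records for people who consent but are never infused. No endpoint, sample size or treatment rule changes.
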